7.2 Study Procedures

7.2.1 Medical history and physical exam

The following needs to be documented:

- For enrollment history and physical exam:
 - complete history of present illness
 - past medical history
 - social history (including smoking history)
 - family history
 - allergy list
 - medication list including dosages and frequency of administration
 - full twelve point review of systems
 - vital signs
 - 10 system physical exam including ECOG PS
 - laboratory data and imaging
 - TURBT pathology specimen report
 - assessment/plan.
- For routine history and physical exam:
 - ECOG PS
 - presence or absence of adverse effects for visits after treatment has started (including management of such events)
 - full twelve point review of systems
 - vital signs
 - 10 system physical exam
 - list of medications including dosages and frequency of administration
 - dose and rate of avelumab being given
 - laboratory data and imaging
 - assessment and plan.
- End of treatment visit must include all the components of a routine history and physical.
- End of study visit must include all the components of a routine history and physical (minus dosage/rate of avelumab) and pathology results from RC.

7.2.2 Radical cystectomy

Radical cystectomy procedure is to be done per standard clinic practice.

In men this procedure involves removal of the bladder and prostate. In women it involves removal of the bladder and oftentimes a hysterectomy as well. In both sexes the procedure is followed by formation of a urinary diversion. The forms of urinary diversion include formation of an ileal conduit (where the ureters empty into the ileum) or formation of an internal reservoir, such as neobladder or continent cutaneous diversion. Relative contraindications to these internal drainage procedures include Tis in the prostatic ducts or a positive urethral margin. (63)

Bilateral pelvic lymph node dissection (LND) is considered standard of care and will be pursued in all patients with no set criteria for dissection template or number of LNs. Unusual circumstances, such as prior LND for another malignancy, significant scarring or inflammation, may preclude a full LND in some patients and will not qualify as a protocol deviation.

7.2.3 Radiographic imaging

- CT and/or MRI imaging will be used to determine suitability for study, adequately stage patients and determine presence or absence of progression.

7.2.4 Clinical laboratory tests

- CBC with diff – will be used to evaluate for autoimmune cytopenias.
- CMP – will be used to evaluate for electrolyte abnormalities, autoimmune nephritis or autoimmune hepatitis.
- UPT – will be performed as indicated in the study calendar for females of CBP.
- Free T4 – to evaluate for autoimmune hypothyroidism or hyperthyroidism.
- TSH – to evaluate for signs of hypophysitis, autoimmune hypothyroidism or hyperthyroidism
- ACTH – this may be used to evaluate for signs of hypophysitis and/or adrenal insufficiency.
- Hepatitis B surface antigen/hepatitis C antibody/hepatitis C RNA panel/HIV – patients with chronic viral infections must be excluded from the administration of immune checkpoint inhibitors (e.g., avelumab) due to lack of published safety data.
- Hemoglobin A1C – to evaluate for worsening of glycemic control, new onset autoimmune diabetes mellitus or worsening of preexisting type I diabetes mellitus.

7.2.5 Follow-up schedule

- Any patient receiving ≥ 1 dose of avelumab will be followed up to 90 days after RC (or end of last cycle of avelumab for those not receiving RC) to evaluate for safety. The indicated follow-up is outlined in the study calendar.
- Those patients evaluable for secondary endpoints will be followed up on study to day 90 after RC as outlined in the study calendar.
- After the safety monitoring period of 90 days post RC those patients who are evaluable for secondary endpoints will be followed off study for recurrence and survival for up to 2 years after RC. This may be done by physician visits/imaging performed approximately every 3 months for those undergoing surveillance at Baylor affiliates or by phone conversations approximately every 3 months for those undergoing surveillance at practices outside of Baylor affiliates.

7.3 Biological Sampling Procedures

Tumor and/or bladder tissue will be collected at two primary time points during the study: at time of TURBT and at time of RC. Peripheral blood will be collected at the time points and for the tests indicated in the study calendar.

7.3.1 Biomarker evaluation methods

Immunohistochemistry:

Concentrations of PD-L1 protein expression on tumor cells or other cell types (e.g. immune cells) will be measured by IHC analysis of FFPE tissues from the TURBT and RC specimens. PD-L1 expression will be assessed using one of the following anti-human-PD-L1 antibodies, depending on initial studies of the relative staining patterns on serial sections: SP142 (Spring Bioscience) (64), SP263 (Ventana Medical Systems), or E1L3N (Cell Signaling Technologies). (65) PD-L1 levels will be evaluated according to the percentage of positively stained cells based on a score ranging from 0 to 3: 0 = <1%; 1 = 1 to <5%; 2 = 5 to <10%; 3 = >10% of cells positive. (66)

FFPE tissue from TURBT and RC specimens will also be stained with primary antibodies for lymphocytic markers CD1d, CD3, CD4, CD5, CD8, CD19 and CD24. This will be

followed by staining with a secondary antibody for horseradish peroxidase and then DAB or blue chromogranin. The results of these lymphocyte IHC stains will be appraised using a semiquantitative scale scored according to the percentage of positively stained cells in tumor or stroma as follows: 0=none, 1 = up to 33% cells in tumor were positive, 2 = 33-66% positive cells and 3=more than 66% cells positive. (67) Tissue sections will be scored by at least two independent staff pathologists.

RNA Extraction from FFPE Tissue:

We have compared three different methodologies head-to-head for extraction of high quality RNA from FFPE tissues, namely ThermoFisher (PureLink™ FFPE RNA Isolation Kit), Clontech (NucleoSpin® totalRNA FFPE) and Covaris (truXTRAC FFPE RNA Kit). Covaris FFPE RNA extraction resulted in the highest quality RNA, sufficient for downstream qPCR and even RNA seq analysis. The main advantages of the Covaris protocol includes its efficiency to completely deparaffinize without using high-temperature enzymatic degradation (which also degrades RNA) and the overall shorter time required to complete the overall protocol. Thus we will extract RNA from FFPE tissue using the protocol for the Covaris truXTRAC FFPE RNA Kit.

qRT-PCR:

RNA will be reverse transcribed according to the manufacturer's instructions with Superscript III First-Strand Synthesis (Invitrogen) to form cDNA. (68) Tagman probes or specific primers will be designed to detect the following genes IFN-γ, TNF-α, TNF-β, T-box protein in B-cells (T-bet), IL-2, IL-10, IL-35, FOXP-3, CTLA-4, LAG-3, PD-L1, Granzyme-A and Perforin-1.

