1.7 Research Hypotheses

- Primary Hypothesis: Avelumab treatment will result in an increase in CD3+CD4+ T-cell and CD3+CD8+ T-cell infiltrates.
- Secondary Hypotheses:
 - Pathological response rate will be comparable to historical controls receiving NA cisplatin based chemotherapy.
 - 2 year disease free survival (DFS) will be better than historical controls not receiving NAC and comparable to historical controls receiving cisplatin based NAC.
 - Avelumab will be safe and tolerable in our patient population.
 - Infiltration of regulatory B-cells will increase with avelumab treatment and increased levels will be associated with less response to treatment.
 - Increased COX-1 and COX-2 levels on transurethral resection of the bladder tumor (TURBT) tissue will be associated with decreased response to avelumab.

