2. STUDY OBJECTIVES

2.1 Primary objective(s)

- To evaluate change in T cell subpopulations (CD8, CD4 and/or CD3) in tumor samples collected pre- and post-treatment with avelumab.

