2.3 Translational endpoints

- To evaluate PD-L1 by IHC and COX-1/COX-2 expression by mRNA in pre- treatment cancer tissues (focusing on epithelial cell expression and immune cell expression).
- To evaluate infiltrating CD3+, CD4+ and CD3+, CD8+ T cells in pre- and post- PD-L1 antibody treated patient cancer tissues by IHC.
- To evaluate change in regulatory B-cell populations with treatment as identified by IHC for CD1d, CD5, CD19 and CD24.
- To evaluate mRNA levels of the following chemokines/cytokines and immune checkpoints on formalin fixed paraffin embedded (FFPE) tissue from pre- and post- treatment specimens: IFN- γ , TNF- α , TNF- β , T-box protein in B-cells (T-bet), IL-2, IL-10, IL-35, FOXP-3, CTLA-4, LAG-3, PD-L1, Granzyme-A and Perforin-1.

[figure not shown]

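### The regulatory B-cell hypothesis cannot be read from the scores specified in section 7.3.1, which define no co-expression measure and no rule combining the four markers

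*Protocol*

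**What the plan says.** Protocol section 1.7 gives this secondary hypothesis: "Infiltration of regulatory B-cells will increase with avelumab treatment and increased levels will be associated with less response to treatment". Section 2.3 gives the matching endpoint: "To evaluate change in regulatory B-cell populations with treatment as identified by IHC for CD1d, CD5, CD19 and CD24".

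Section 7.3.1 is where the measurement is fixed. FFPE tissue from the TURBT and the cystectomy is "stained with primary antibodies for lymphocytic markers CD1d, CD3, CD4, CD5, CD8, CD19 and CD24", "followed by staining with a secondary antibody for horseradish peroxidase and then DAB or blue chromogranin". The stains are then graded on a four-step scale of the percentage of positive cells: 0 for none, 1 for up to 33%, 2 for 33 to 66%, 3 for more than 66%. At least two pathologists score the sections.

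For T cells there are two wordings. The primary hypothesis in 1.7 is that "Avelumab treatment will result in an increase in CD3+CD4+ T-cell and CD3+CD8+ T-cell infiltrates", and 2.3 plans "To evaluate infiltrating CD3+, CD4+ and CD3+, CD8+ T cells in pre- and post- PD-L1 antibody treated patient cancer tissues by IHC". The primary objective in 2.1 is "To evaluate change in T cell subpopulations (CD8, CD4 and/or CD3) in tumor samples collected pre- and post-treatment with avelumab", and the sample-size text in 10.1 lists the same markers in the same way.

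Section 10.2 plans paired tests for changes from before to after treatment, and a descriptive summary of how translational results relate to response.

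**The concern.** Section 2.3 names one cell population and four markers that identify it. On the natural reading, a regulatory B cell is a cell that carries those markers together. A grade for each stain says how common each marker is, but not how often the markers sit on the same cell. Section 7.3.1 mentions no dual or multiplex stain, no registration of serial sections and no rule that turns four grades into one measure. The mRNA panel in 2.3 and 7.3.1 does not fill the gap: it is run on RNA extracted from tissue and does not identify a B-cell phenotype.

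At stake is a stated secondary hypothesis. If the plan is followed as written, changes in four single-marker grades could be put through the paired tests of 10.2, set against response, and reported as changes in regulatory B cells. Later analysis cannot recover co-expression that was never recorded, so this is a matter for the protocol and not one that can wait for an analysis plan.

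**Working it through.** **Inputs.** The score limits are those of 7.3.1: score 0 is 0%; score 1 is above 0% and up to 33%; score 2 is 33% to 66%; score 3 is above 66% and up to 100%. The number of markers is k = 4 for regulatory B cells (2.3) and k = 2 for CD3 with CD4 or CD3 with CD8 (1.7, 2.3). I assume one grade per marker and the same cells as denominator for every marker. If denominators differ, the grades say even less.

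**Formula.** For marker shares p1 to pk, the share of cells positive for all k markers lies between max(0, sum of p − (k − 1)) and the smallest p. With only categories recorded, use the lower category limits on the left and the upper limits on the right.

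| Recorded scores | Lower bound | Upper bound |
|---|---|---|
| Four markers, all 1 | max(0, 0 − 3) = 0% | 33% |
| Four markers, all 2 | max(0, 4 × 0.33 − 3) = max(0, −1.68) = 0% | 66% |
| Four markers, all 3 | max(0, 4 × 0.66 − 3) = max(0, −0.36) = 0% | 100% |
| Two markers, both 1 | max(0, 0 − 1) = 0% | 33% |
| Two markers, both 2 | max(0, 2 × 0.33 − 1) = max(0, −0.34) = 0% | 66% |
| Two markers, both 3 | max(0, 2 × 0.66 − 1) = 32% | 100% |

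**Reading for B cells.** Some four-way overlap is forced only when the four percentages sum to more than 300%, for example when all exceed 75%. Score 3 begins at 66% and does not separate 67% from 80%, so the lower bound is 0% for every possible set of four scores. Only a score of 0 on some marker settles the matter, by showing that the population is absent.

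To show an increase, the lower bound after treatment must exceed the upper bound before it. To show a decrease, the reverse must hold. Since the lower bound is always 0%, no pair of score sets can establish a change in either direction. Two patients with identical scores can also have very different populations, so the association with response is not readable either.

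**The plan's own figure.** Section 10.1 states about 80% power for 10 pairs, a change of 1 SD, r of at least 0.5 and two-sided alpha of 5%. At r = 0.5 the SD of the difference is SD × √(2 × (1 − 0.5)) = 1 SD. With 9 degrees of freedom and noncentrality √10 = 3.16, the paired t-test has 80.3% power. The figure reproduces, and nothing in this point alters it.

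**The case against.** Four things can be said on the other side.

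- **Section 7.3.1 does not say that each marker is scored on its own.** It lists antibodies, names two chromogens and grades the stains. A reader might infer that co-staining is ruled out. The documents do not support that: it is neither stated nor excluded. Nor does 2.3 use the word co-expression. This stands, so the claim is limited to the readout as specified. Even so, if co-staining is intended, the protocol still gives no score for cells positive for several markers.
- **The primary endpoint is not in trouble.** A reader might infer from the double-positive wording in 1.7 and 2.3 that the primary question cannot be answered. It can: 2.1 and 10.1 accept the T-cell markers singly, and the 7.3.1 grades serve that objective. Only a mismatch of wording remains.
- **The bounds are extremes, not an estimate of likely error.** True, and two markers both at score 3 do carry information (at least 32% double positive). For four markers, however, the grades never move the lower bound off zero.
- **This is a 10-patient pilot, and 10.2 only summarises correlation with response descriptively.** This limits the harm, and formal confirmation of the association was never planned. A descriptive summary still needs a defined variable, and change from baseline is to be tested.

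A further argument would be that some of the four markers also occur on T cells or tumour cells, so that a T-cell influx could pass for a rise in regulatory B cells. The documents say nothing on marker specificity, and the point does not need it.

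**Conclusion.** The concern holds for regulatory B cells. As specified in 7.3.1, the readout yields no variable for the population named in 1.7 and 2.3. With all four markers at the top score, the co-expressing share can be anything from 0% to 100%, and no pair of recorded scores can establish a change. This rests on two readings: that the four markers in 2.3 jointly define the population, and that 7.3.1 yields one grade per marker. Both are natural readings, but neither is spelled out.

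For T cells the fault is minor: 1.7 and 2.3 name double-positive cells, while 2.1 and 10.1 name single markers. The documents do not support the inference that the primary endpoint cannot be scored, and no power or alpha figure changes. The trial can run as planned; what needs correcting is what it may claim about regulatory B cells.

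**What to change.** In sections 1.7 and 2.3, report CD19, CD1d, CD5 and CD24 as separate descriptive single-marker scores, and state that no regulatory B-cell conclusion will be drawn from them. The exception is if 7.3.1 is amended to define a co-expression readout, in which case it should say how cells positive for all four markers are identified and scored.

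As a minor edit, align the CD3+CD4+ and CD3+CD8+ wording in 1.7 and 2.3 with the single-marker wording of 2.1 and 10.1.

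The relabelling costs only wording in 1.7 and 2.3, but the secondary hypothesis on regulatory B cells is then given up in its present form and the trial makes a narrower claim. Keeping the hypothesis through a co-expression readout would add a laboratory procedure; the protocol gives no information from which to judge its feasibility or cost. Sample size, alpha and the primary analysis stay as they are.

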10. STATISTICAL METHODS

10.1 Study design and sample size

This is a single arm, non-randomized window of opportunity study to see the change in T cell subpopulations (CD8, CD4 and/or CD3) in tumor samples collected pre- and post-treatment with avelumab. Assuming that pre- and post-treatment values within patients are moderately correlated ($r \geq 0.5$), then 10 patients with paired pre- and post-treatment samples will provide ~80% power to detect a 1 standard deviation change in T cell populations (alpha=5% two-tailed).

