10.2 Statistical analysis

To see the change in T cells pre- and post-treatment, paired t-test or nonparametric Wilcoxon signed rank test will be used after checking its normality.

Pathological response rate will be estimated along with 95% confidence interval. Two year disease free survival will be calculated using Kaplan-Meier survival curves with estimates of median and 95% confidence interval. Patients who are decided not to be evaluable for the primary outcome will be considered evaluable for the safety analysis and secondary outcomes, such patients will be summarized descriptively. The correlation of translational studies with response parameters will be summarized descriptively. Changes from pre- and post- treatment will be assessed using paired tests. SAS software will be used for all statistical analyses.

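### The ~80% power in section 10.1 is not assured for the 0-3 score in which section 7.3.1 records the primary T-cell readout

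*Protocol*

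**What the plan says.** The primary objective (Protocol 2.1) is "To evaluate change in T cell subpopulations (CD8, CD4 and/or CD3) in tumor samples collected pre- and post-treatment with avelumab". The matching hypothesis (1.7) is directional: "Avelumab treatment will result in an increase in CD3+CD4+ T-cell and CD3+CD8+ T-cell infiltrates". Section 2.3 names the assay: "To evaluate infiltrating CD3+, CD4+ and CD3+, CD8+ T cells in pre- and post- PD-L1 antibody treated patient cancer tissues by IHC".

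Section 7.3.1 says how the lymphocyte stains are read. They are "appraised using a semiquantitative scale scored according to the percentage of positively stained cells in tumor or stroma", with levels "0=none, 1 = up to 33% cells in tumor were positive, 2 = 33-66% positive cells and 3=more than 66% cells positive", by at least two pathologists. The protocol specifies no recorded percentage, cell count or density for CD3, CD4 or CD8, and its qRT-PCR gene list does not include them. As written, the primary variable is the 0-3 score.

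Section 10.1 assumes that "pre- and post-treatment values within patients are moderately correlated" (r of at least 0.5) and states that "10 patients with paired pre- and post-treatment samples will provide ~80% power to detect a 1 standard deviation change in T cell populations" at two-sided 5%. Section 10.2 gives the test: "paired t-test or nonparametric Wilcoxon signed rank test will be used after checking its normality".

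**The concern.** A power figure for a 1-SD change in a normally distributed value need not carry over to a coarse score. Three of the four levels are about a third of the scale wide, so a rise from 5% to 30% positive cells counts as no change. How much power is lost depends on where tumours start and how widely they are spread, and section 10.1 gives neither. It also does not say whether the SD is that of the percentage or of the score.

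This is the only power statement in the trial. If infiltrates sit narrowly below 33% with few tumours scored none, a 1-SD rise in the percentage would usually be missed. If many tumours start at none, the loss may be small. The protocol does not say which case applies, so a reader cannot tell what a null result means. Percentages that were never written down cannot be recovered at the analysis stage.

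**Working it through.** **1. The plan's own figure.** Inputs from 10.1: n = 10 pairs, a change of 1 SD, r = 0.5, two-sided 5%. The SD of the difference is SD × √(2(1 − r)), so the standardised change is dz = 1/√(2(1 − r)).

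- r = 0.5: dz = 1, noncentrality √10 = 3.16 on 9 df, power 0.803.
- r = 0.6: dz = 1.118, power 0.881.
- r = 0.7: dz = 1.291, power 0.951.

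At r = 0.5 the normal approximation gives 0.885 and a one-sided t-test 0.898, so the stated figure matches the two-sided paired t-test. The exact signed-rank test on the same normal data gives 0.784 (40,000 simulated trials).

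**2. What each test needs on the score.** The exact signed-rank test with zeros dropped has a smallest two-sided p of 2/2^k when k patients change: 0.0625 for k = 5 and 0.031 for k = 6. At least 6 of 10 must change level. By t-test, 4 of 10 rising one level is enough (mean 0.4, SD 0.516, t = 0.4/(0.516/√10) = 2.45, against a critical value of 2.26).

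Suppose each patient rises one level with probability 0.5, so mean 0.5, SD 0.5 and dz = 1. Power is P(at least 4 of 10) = 0.83 by t-test but P(at least 6 of 10) = 0.38 by exact signed-rank. The normality check matters too. Five patients at +1 and five at 0 give t-test p = 0.015, Shapiro-Wilk p = 0.0003 and signed-rank p = 0.0625. Shapiro-Wilk and the exact test are assumptions here; 10.2 names neither.

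**3. If the 1 SD is on the underlying percentage.** Every baseline is assumed, as mean/SD in percentage points. Shapes are beta or clipped normal, none means 0.5% or less, there is one score per sample, and each cell has 4,000 simulated trials at r = 0.5. The rule column takes the signed-rank test if Shapiro-Wilk p < 0.05 and the t-test otherwise.

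| Assumed baseline | Paired t | Exact signed-rank | Rule |
|---|---|---|---|
| Narrow, below 33% (10/5, 15/10, 20/10) | 0-0.36 | 0-0.06 | 0-0.06 |
| 20/15 | 0.40-0.55 | 0.12-0.24 | 0.12-0.25 |
| Wide (30/20, 40/20, 20/25) | 0.57-0.66 | 0.35-0.48 | 0.37-0.55 |
| Strongly skewed beta (10/20, 15/25; 43-53% scored none) | 0.78 | 0.64-0.65 | 0.69-0.71 |
| Clipped normal, same means and SDs (28-32% none) | 0.61-0.65 | 0.38-0.46 | 0.41-0.53 |

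Five or fewer patients change level in all simulated trials at 10/5, in 0.90-0.94 of them at 20/10 and in 0.34-0.39 at 30/20.

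At r = 0.7 the t-test gives 0-0.38 (narrow), 0.46-0.66 (20/15), 0.71-0.77 (30/20 and 40/20), 0.81 (20/25) and 0.87-0.88 (skewed beta), against 0.951 for the uncut normal value. Averaging two readers' scores (assumed error SD 5 points, r = 0.5) gives 0-0.41, 0.63-0.72 and 0.66-0.82 by t-test for narrow, wide and skewed beta.

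**4. If the 1 SD is on the score.** A latent normal value is cut at assumed baseline shares and shifted until the mean score rises by 1 baseline score SD. Score correlation is about 0.5.

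| Shares at 0/1/2/3 (%) | Paired t | Exact signed-rank | Rule |
|---|---|---|---|
| 25/25/25/25 | 0.92 | 0.79 | 0.81 |
| 10/40/40/10 | 0.83 | 0.65 | 0.70 |
| 20/50/20/10 | 0.78 | 0.60 | 0.67 |
| 50/35/10/5 | 0.70 | 0.52 | 0.59 |
| 10/70/15/5 | 0.67 | 0.41 | 0.45 |
| 3/87/9/1 | 0.40 | 0.10 | 0.10 |

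At score correlation 0.6 to 0.7, paired-t power is about 0.77-0.97 for the first five rows and exact signed-rank about 0.50-0.87. The last row stays low (0.51 by t-test at 0.6).

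**The case against.** Four arguments go the other way.

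- **The correlation is a floor.** Section 10.1 assumes r of at least 0.5, so 0.803 is its lowest case. With the SD read on the score, the t-test reaches or comes close to 80% at r of 0.6 to 0.7 for five of the six assumed baselines, including two that are not broadly spread. This stands. A reader might infer from the narrow-baseline figures that the score reaches 80% only in special cases, or that power is generally lost. The documents do not support that, because they fix neither the correlation above 0.5 nor the scale of the SD.
- **Section 10.1 never says the value is continuous.** True. That is inferred from the effect in SD units and from the calculation that reproduces ~80%. Reading the SD on the score is at least as natural, which is why both readings are shown.
- **The baselines are assumed.** They have to be, because the protocol gives none. The near-zero figures come from cases such as 10/5, where 1 SD is only 5 percentage points. The range shows that power is undetermined; it is not an estimate of this trial's power.
- **This is a 10-patient pilot, and a statistical analysis plan may settle the test and how readers are combined.** No decision rule hangs on the primary result, and those details are not held against the protocol. But the power claim and the recorded scale are both fixed in the protocol, and they do not fit each other without further assumptions.

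**Conclusion.** The point holds as a mismatch between sections 10.1 and 7.3.1, and it should be fixed before the slides are scored. The arithmetic in 10.1 is right for a normally distributed value analysed by paired t-test. For the recorded score, ~80% is not assured.

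With 1 SD on the percentage at r = 0.5 and one score per sample, power is about 0-0.78 by t-test and 0-0.65 by exact signed-rank, lowest when infiltrates sit narrowly below 33%. With 1 SD on the score it is about 0.40-0.92 by t-test and 0.10-0.79 by exact signed-rank at r = 0.5. At r = 0.6 to 0.7 these become about 0.77-0.97 and 0.50-0.87, except when nearly all tumours start at one level.

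The mismatch and the 6-of-10 requirement of the exact test do not depend on the assumed baselines. The size of any loss depends on them entirely.

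**What to change.** - **7.3.1:** have the same pathologists write down the estimated percentage of positive cells for each T-cell marker beside the band, which is already assigned from that percentage.
- **10.2:** make the paired change in the readers' mean percentage the primary analysis under one pre-named test, for example the exact signed-rank test. Keep the score as descriptive.
- **10.1:** name the variable, the scale of the SD and the test, and restate the power. The exact signed-rank test gives about 78% on normal data at r = 0.5 before reader error. With two readers and an assumed error SD of 5 points it gives 0.70-0.76 at a baseline SD of 15 or more, 0.68-0.70 at SD 10 and about 0.50 at SD 5. The change does not restore 80%, so 10.1 needs rewording either way.
- **If the score stays primary:** replace the ~80% with the power under a stated score distribution, correlation and test.

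The cost is wording in three sections and one extra number per marker, section and reader, with no extra slides, stains or patients. The downside is that estimated percentages carry reader error. With a strongly skewed baseline they gain nothing over the score analysed by t-test (0.71-0.73 against 0.78, one reader). Their advantage is power that depends far less on where infiltrates sit.
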